10.3. Data Analysis Considerations

10.3.1. Analysis Populations

Three subject populations will be identified.

Total Population: This population will comprise of all subjects screened and for whom a record exists on the study database and will be used for the tabulation and listing of reasons for withdrawal before randomization.

Intent-to-Treat (ITT) Population: The ITT Population will comprise all subjects randomized to treatment and who received at least one dose of trial medication. Randomized subjects will be assumed to have received trial medication unless definitive evidence to the contrary exists. This will constitute the primary population for all analyses of efficacy measures and safety measures. Outcomes will be reported according to the randomized treatment allocation.

Per Protocol (PP) Population: The PP Population will consist of all subjects in the ITT Population who do not have full protocol deviations. Protocol deviations can either be full or partial. Subjects with only partial deviations will be considered part of the PP population but their data will be excluded from the date of their deviation until either the end of the study or the end of the treatment period in which the deviation occurred. The decision to exclude a subject, or part of their data, from the PP Population will be made prior to breaking the blind. Protocol deviations that will lead to full or partial exclusion from the PP population will be detailed in the Reporting and Analysis Plan (RAP). This population will be used for confirmatory analyses of the primary efficacy endpoint only.

10.3.2. Analysis Data Sets

Details of the derived data in analysis datasets to be created will be given in the RAP.

10.3.3. Treatment Comparisons

10.3.3.1. Primary Comparisons of Interest

The primary treatment comparison is the comparison of group means for the FF/VI combination and FP for the primary endpoint of maximal percent decrease in FEV₁ from pre-exercise at 12 hrs post-evening dose at the end of the 2-week treatment period. This comparison is to be performed using the ITT Population.

10.3.3.2. Other Comparisons of Interest

The primary treatment comparison of FF/VI combination versus FP for the primary endpoint will also be performed for the PP population.

In addition FF/VI combination will be compared to FP for the secondary and other efficacy endpoints.

10.3.4. Interim Analysis

No interim analysis is planned.

10.4. Key Elements of Analysis Plan

Where possible, data from subjects who withdraw prematurely from the study will be included in any analyses. Specific details for inclusion will be detailed in the RAP but, in general, if a subject has completed a treatment period, including both exercise challenges and FEV₁ evaluations, then the data for that period will be included in the analysis.

Specifically if a subject has completed the first exercise challenge at 12 hours post-dose, as well as the FEV₁ evaluations after this challenge, but has not completed the second exercise challenge at 23 hours post-dose, then the data for the 12 hour post-dose time point will be included, but will not be carried forward to replace the missing 23 hour time point.

Any tests for interactions will be 2-sided at the 10% level of significance. In all cases, if any assumptions of the proposed methods of analyses are not met, alternative methods of analyses will be used.

The baseline FEV₁ for all endpoints will be the pre-treatment FEV₁ value obtained at the start of each Treatment Period (Visit 2 or Visit 5).

10.4.1. Efficacy Analyses

All efficacy data will be summarized using means, standard deviations, medians and ranges for continuous variables and frequencies and percentages for categorical variables.

10.4.1.1. Primary Analysis

The primary efficacy end point is maximal percent decrease from pre-exercise FEV₁ following exercise challenge at 12 hours post-dose following two weeks of treatment. Maximal percent decrease will be defined as the percent change from pre-exercise FEV₁ to the minimum FEV₁ collected within one hour following exercise challenge at 12 hours post-dose. Pre-exercise FEV₁ will be defined as the FEV₁ value collected prior to the exercise challenge test at 12 hours post-dose.

The primary analysis is a comparison of the estimated means of the two treatment groups in maximal percent decrease in FEV₁ from pre-exercise at 12 hrs post-dose using a LMM to adjust for covariate effects. The LMM will include the following covariates: treatment, subject-level mean of the pre-treatment FEV₁ period baselines (mean of the 2 period baselines per subject), centered period-level baseline FEV₁ (period baselines centered using subject-level mean of the pre-treatment FEV₁ period baselines), gender, age, treatment period and smoking history as fixed effects, and a random intercept for each subject.

Details will be provided in the RAP of alternative analyses methods to be used in the event that distributional assumptions do not hold (e.g. if the distribution appears to be heavily skewed).

Mean post-exercise minimum FEV₁ measurements and mean maximal percent decrease from pre-exercise FEV₁ will be summarized with descriptive statistics by treatment group. Summaries and analyses for the primary endpoint will be provided for both the ITT and PP populations.

10.4.1.2. Secondary Analyses

Summaries and analyses for secondary endpoints will be provided for the ITT population.

Maximal percent decrease from pre-exercise FEV₁ following exercise challenge (at 23 hours post-dose at the end of the 2-week treatment period):

This endpoint will be summarized and analyzed as for the primary endpoint of maximal percent decrease from pre-exercise FEV₁ following exercise challenge at 12 hours post-dose.

Proportion of subjects with a 30 minute post-challenge FEV₁ that was no more than 5% lower than their pre-exercise FEV₁ following the exercise challenge at 12 hours and 23 hours post evening dose at the end of the 2-week treatment period

This endpoint will be analysed using a logistic regression model separately for the 12 and 23 hour challenges using the covariates baseline FEV₁, treatment group, gender, age, and smoking history.

Weighted mean 0-60 minutes for percentage decrease from pre-exercise FEV₁ after exercise (at 12 hours and 23 hours post-dose at the end of the 2-week treatment period):

A comparison will be made of the estimated means of the two treatment groups in for weighted mean 0-60 minutes of the percentage decrease in FEV₁ from pre-exercise at 12 and 23 hrs post-dose using a LMM to adjust for covariate effects. The LMM will include the following covariates: treatment, subject-level mean of the pre-treatment FEV₁ period baselines (mean of the 2 period baselines per subject), centered period-level baseline FEV₁ (period baselines centered using subject-level mean of the pre-treatment FEV₁ period baselines), gender, age, treatment period and smoking history as fixed effects, and a random intercept for each subject.

10.4.1.2.1. Other Efficacy Analyses

Other measures of efficacy include the evaluation of a categorical treatment response evaluating the percentage of subjects who demonstrate a decrease from pre-exercise challenge FEV₁<10%, a decrease $\geq 10\%$ to <20%, or a decrease $\geq 20\%$, and an evaluation of maximal percent decrease from treatment period baseline in FEV₁ (period baseline) following exercise challenge (at 12 hours and 23 hours post-dose). Additional endpoints

include evaluation of physical activity monitoring the ACQ-5 score, and the proportion of subjects with a 5 minute post-challenge FEV₁ that was no more than 5% lower than their pre-exercise FEV₁ following the exercise challenge at 12 hours and 23 hours post evening dose at the end of the 2-week treatment period (repeat for the 10, 15, 45 and 60 minute time points).

10.4.2. Safety Analyses

Safety will be assessed with clinical adverse events and asthma exacerbations.

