Corticosteroid associated eye disorders	
This is considered a class effect of ICS. Preclinical studies showed FF at high dose comparable to other high dose corticosteroids. In study HZA106839 (FF/VI, FF and FP in subjects with asthma), formal ophthalmic assessments were conducted (including LOCS III evaluations for ocular opacities) throughout the study. This study showed no apparent effects on lens opacification, compared to baseline. During studies in both subjects with asthma and COPD, no associated affect on ocular disorders was observed.
	
Subjects will be informed about the risk of corticosteroid associated eye disorders in the informed consent. Subjects will be advised to seek medical treatment if any signs of eye disorder occur. Investigators are made aware of the potential for this class effect in Section 5.3.3.7 (Ophthalmic Effects) of the IB.

Study Design and Procedures		
Exercise-induced bronchoconstriction following exercise challenge testing	This study specifically recruits a study population which demonstrates a minimal level of exercise-	Exercise challenges may be stopped at any time during the assessment for worsening asthma. (Guidelines for treatment are provided in the

Potential Risk of Clinical Significance	Summary of Data/Rationale for Risk	Mitigation Strategy
	induced bronchoconstriction ($\geq 20\%$ decrease from their pre-exercise FEV ₁). However, more severe bronchoconstriction is possible following exercise challenge testing.	
study reference manual [SRM].)
 
If a subject's FEV₁ decreases to $\geq 40\%$ from their pre-exercise FEV₁ following exercise challenge, he/she must receive rescue therapy. If he/she requires rescue therapy with anything other than MDI (Metered Dose Inhaler) or nebulized albuterol/salbutamol or ipratropium (secondarily) following the exercise challenge assessment, he/she will not be allowed to continue in the study.
 
Subjects will be monitored until their FEV₁ reaches $\geq 95\%$ of their pre-exercise FEV₁. Rescue Albuterol/salbutamol may be given during recovery.

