7.10. Concomitant Medications and Non-Drug Therapies

The names, doses, and regimens of the asthma medications taken during the 12 weeks prior to Visit 1 must be recorded in the Concomitant Medications section in the eCRF.

All concomitant medications taken during the study will be recorded in the eCRF. The minimum requirement is for the reporting of the drug name and dates of administration. Study provided albuterol/salbutamol should NOT be recorded in the eCRF.

Asthma medications taken after the final clinic visit will not be recorded in the eCRF.

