8.3.1.1. Target FEV₁ Calculations

Three target FEV₁ values will be calculated from the pre-exercise FEV₁ to determine subject eligibility and for monitoring the safety of the subject prior to exercise challenge testing:

1. The FEV₁ value that represents a $\geq 20\%$ decrease in FEV₁, which is the eligibility criterion.
2. The FEV₁ value that represents a $\geq 40\%$ decrease in FEV₁, which will serve as an alert for severe bronchoconstriction and need for administering rescue treatment.
3. The FEV₁ value that represents a $\geq 95\%$ recovery of the FEV₁ result.

Subjects should be monitored until they reach a recovery level where their FEV₁ value represents a 95% recovery of the pre-exercise FEV₁ result. Additional spirometry and rescue medication may be used as needed (See Section [8.3.2.1](#)).

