- The disease/disorder being studied or expected progression, signs, or symptoms of the disease/disorder being studied, unless more severe than expected for the subject's condition.
 - Medical or surgical procedure (e.g., endoscopy, appendectomy): the condition that leads to the procedure is an AE.
 - Situations where an untoward medical occurrence did not occur (social and/or convenience admission to a hospital).
 - Anticipated day-to-day fluctuations of pre-existing disease(s) or condition(s) present or detected at the start of the study that do not worsen.

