8. SAFETY ANALYSES

8.1. Safety Analyses

8.1.1. Overview of Planned Safety Analyses

The safety analyses will be based on the ITT population, unless otherwise specified.

[Table 5](#) provides an overview of the planned analyses, with further details of data displays being presented in [Appendix 13: List of Data Displays](#).

Table 5 Overview of Planned Safety Analyses

Display Type	Data Displays Generated		
	Table	Figure	Listing
Adverse Events			
Overview	Y		
AEs for Subjects not in ITT			Y ^[2]
Pre-Treatment AEs			Y
On-Treatment AEs	Y ^[3]		Y
Post-Treatment AEs	Y		Y
Most Frequent On-Treatment AEs (≥3% after rounding)	Y		
Top Ten Most Common On-Treatment AEs	Y		
Drug-Related AEs	Y		
Drug-Related SAEs	Y		
AEs Leading to Withdrawal	Y		Y
On-Treatment SAEs	Y		Y
Post-Treatment SAEs	Y		Y
Common On-Treatment Non-Serious AEs (≥3% without rounding including event numbers and drug-related event numbers)	Y		
On-Treatment SAEs (including event numbers and drug-related event numbers)	Y		
On-Treatment Fatal AEs (including event numbers and drug-related event numbers)	Y		
Post-Treatment Fatal SAEs (including event numbers and drug-related event numbers)	Y		
AEs of Special Interest	Y ^[1]		
SAEs of Special Interest	Y		
Relationship of AE System Organ Class, Preferred Term and Verbatim Text	Y		
Record of all Preferred Term's That Could Have Mapped to Special Interest Terms	Y		
Pneumonia			
On-Treatment Pneumonia	Y		Y
Post-Treatment Pneumonia	Y		Y
Chest X-ray			Y
Severe Asthma Exacerbations			
Severe Asthma Exacerbations	Y ^[3]		Y

Display Type	Data Displays Generated		
	Table	Figure	Listing
Other			
Vital Signs	Y		Y
Change from Baseline in Vital Signs	Y		
Family History of CV Risk Factors	Y		Y
IP Inhaler Malfunctions			Y

NOTES :

- Y = Yes display generated.
- [1]: Display will be based on the ITT population and repeated for the ITT (12-17 Years Old) population
- [2]: Display will be based on the inverse of the ITT population i.e. all subjects not in the ITT population
- [3]: Display will be based on the ITT population and repeated for the ITT (12-17 Years Old) population and also for the ITT (15 Years or Older) population

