10.6.3. Efficacy

Primary Endpoint

Maximal % Decrease from Pre-Exercise FEV₁ Following 12 Hour Challenge at Day 14

The primary endpoint will be derived as follows:

$$\frac{\text{Pre-Exercise FEV}_1 - \text{Minimum Post Exercise FEV}_1}{\text{Pre-Exercise FEV}_1} \times 100$$

Where pre-exercise FEV₁ will be defined as the FEV₁ value collected immediately prior to the exercise challenge.

And the minimum post exercise FEV₁ will be the smallest FEV₁ value recorded from the planned post-challenge time points (5, 10, 15, 30, 45 and 60 minutes) using only those with an actual time that is no more than 65 minutes after the challenge stop time.

The minimum post exercise FEV₁ will only be calculated if there are at least the following non-missing FEV₁ values:

- A post-exercise measurement with an actual time of ≤ 17 minutes
- A post-exercise measurement with an actual time of ≥ 25 and ≤ 50 minutes

If there are not values meeting both of these criteria available then the endpoint will not be calculated and will be treated as missing.

Secondary and Other Endpoints

Maximal % Decrease from Pre-Exercise FEV₁ Following Exercise Challenge

Maximal percent decrease from pre-exercise FEV₁ will be derived for other time points in the same way as for the primary endpoint.

Maximal Decrease from Pre-Exercise FEV₁ (L) Following Exercise Challenge

Maximal decrease from pre-exercise FEV₁ (L) will be derived as:

$$\text{Pre-Exercise FEV}_1 - \text{Minimum Post Exercise FEV}_1$$

Where pre-exercise FEV₁ and minimum post-exercise FEV₁ are defined in the same way as for the primary endpoint and the same minimum number of non-missing FEV₁ values are required for the endpoint to be calculated.

Maximal % Decrease from Period Baseline FEV₁ Following Exercise Challenge

Maximal percent decrease from period baseline FEV₁ will be derived as:

$$\frac{\text{Period Baseline FEV}_1 - \text{Minimum Post Exercise FEV}_1}{\text{Period Baseline FEV}_1} \times 100$$

Where minimum post-exercise FEV₁ is defined in the same way as for the primary endpoint and the same minimum number of non-missing FEV₁ values are required for the endpoint to be calculated.

Secondary and Other Endpoints
Maximal Decrease from Period Baseline FEV₁ (L) Following Exercise Challenge
Maximal decrease from period baseline FEV ₁ (L) will be derived as:
Period Baseline FEV₁ – Minimum Post Exercise FEV₁

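### No planned display counts post-challenge FEV₁ falls of 40% or more by treatment, although the protocol makes that level its alert for severe bronchoconstriction

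*Protocol*

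**What the plan says.** **The risk.** Protocol 5.6.1 lists bronchoconstriction after the challenge among the risks of the study procedures and warns: "However, more severe bronchoconstriction is possible following exercise challenge testing". Protocol 8.3.1.1 derives target values from the pre-exercise FEV₁. The one for a fall of at least 40% is the value "which will serve as an alert for severe bronchoconstriction and need for administering rescue treatment". Protocol 6.4.1 and 8.3.2.1 make rescue mandatory at that level.

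**The safety analysis.** Protocol 10.4.2 reads: "Safety will be assessed with clinical adverse events and asthma exacerbations". SAP 8.1.1 adds: "The safety analyses will be based on the ITT population, unless otherwise specified". SAP Table 5 and Tables 3.1 to 3.28 (SAP 10.13.5) cover adverse events, pneumonia, severe exacerbations and vital signs. None is based on FEV₁.

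**The efficacy analysis.** SAP Tables 2.1 and 2.10 summarise the maximal percent fall by treatment. SAP 7.2.2.4 sorts falls into three categories, the worst being 20% or more. For the maximal fall, SAP 10.6.3 sets a condition: "The minimum post exercise FEV₁ will only be calculated if there are at least the following non-missing FEV₁ values". These are one reading at 17 minutes or earlier and one between 25 and 50 minutes.

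**The concern.** Subjects are selected for a fall of at least 20% while taking FP, and then repeat the challenge six times on study treatment. A fall of 40% or more is the harm these challenges are most likely to cause, and protection against it is the safety side of the trial's own question. The protocol has already fixed the threshold, and the readings are already collected. If nothing tabulates them, the report can give AE and exacerbation counts by treatment without saying how often this named event occurred on each. The SAP presents itself as covering all output for the final report, so the count is unlikely to be added by default.

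**Working it through.** **Step 1. Follow one event through the planned displays.** Take a fall of 40% or more that study albuterol reverses.

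| Route | Rule | Counts this event? |
|---|---|---|
| AE tables | Protocol 13.5.1 excludes "The disease/disorder being studied or expected progression, signs, or symptoms of the disease/disorder being studied, unless more severe than expected for the subject's condition". The same section counts a pre-existing condition that becomes more frequent or intense as an AE. | Only by site judgement; no FEV₁ level is given |
| SAE tables | Protocol 13.5.2: intensively treated allergic bronchospasm is an example, but an event that is not an AE cannot be an SAE. | Only if first judged an AE |
| Special-interest AEs | Protocol 8.4.1.3 points to Section 5.6.1. SAP 8.2.1.1 restricts the table to events of interest for FF or VI, and SAP 10.6.4 leaves the terms to be agreed before unblinding. | Only if reported as an AE and its term is chosen |
| Severe exacerbations | Protocol 6.4.1 and 8.4.2: at least three days of systemic steroids, or hospital or emergency care that needed them. | No |
| Withdrawal | Protocol 6.4.1: after a challenge, required if rescue goes beyond albuterol/salbutamol or ipratropium. | No |
| Rescue use | Protocol 7.10: "Study provided albuterol/salbutamol should NOT be recorded in the eCRF". | No |
| Efficacy categories | SAP 7.2.2.4: worst category is 20% or more, the same level required for entry in Protocol 6.2.1. | Pooled: 21% and 55% fall together |
| Maximal-fall summaries | SAP 10.5.3: mean, SD, median, minimum, maximum. | Shows the extreme, not the number |
| Listing 8 | Raw lung function data. | Listed, not counted |

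**Step 2. The missing-reading rule.** If serial spirometry stops before 25 minutes, the maximal fall is set to missing (SAP 10.6.3 and 10.7.2), however deep the earlier reading. In the Per Protocol analysis of the primary endpoint, SAP 10.1.1 also sets to missing any FEV₁ taken within 6 hours after rescue. Rescue before 25 minutes would, as written, remove the required later reading there too.

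**Step 3. Number of challenges.** The plan states no figure for falls of 40% or more. Its subject numbers reproduce: 275 × 0.80 = 220; 220 × 0.30 = 66; 66 × 0.85 = 56.1. Visits 3 and 6 have one challenge each, and Visits 4 and 7 have two each: 2 × 1 + 2 × 2 = 6 per subject, or 3 per treatment. That gives 56 × 3 = 168 challenges per treatment among completers, and at most 66 × 3 = 198.

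**Step 4. How many events might go uncounted.** The documents give neither a rate nor a distribution of falls, so both calculations rest on assumptions.

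*Assumed proportion p of subjects affected on a treatment* (expected number 56p; chance of at least one 1 − (1 − p)^56):

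| p | Expected subjects | Chance of at least one |
|---|---|---|
| 1% | 0.6 | 43% |
| 2% | 1.1 | 68% |
| 5% | 2.8 | 94% |
| 10% | 5.6 | 99.7% |

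*Assumed normal maximal fall* (expected challenges = 168 × [1 − Φ((40 − mean)/SD)]). The plan's within-subject SD of 8% is a floor for the total SD:

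| Mean fall | SD 8 | SD 11 | SD 14 |
|---|---|---|---|
| 15% | 0.1 | 1.9 | 6.2 |
| 20% | 1.0 | 5.8 | 12.9 |
| 25% | 5.1 | 14.5 | 23.9 |

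If none of 56 subjects had such a fall, the one-sided upper 95% bound on the rate would be 1 − 0.05^(1/56) = 5.2%.

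**The case against.** The strongest reply is that the harm is not hidden. Maximal percent fall is the primary endpoint at 12 hours and a secondary endpoint at 23 hours. Both are summarised by treatment with minimum and maximum, and SAP 7.2.2.1 also analyses the Day 1 challenge. An evaluable subject with a fall of 40% or more would push the maximum for that treatment to at least 40%, and the main comparison estimates the mean difference in falls. This stands, and it rules out reading the plan as leaving the data only in a raw listing. It does not supply a count: one such fall and eight can give the same maximum.

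A reader might also infer that these events are shut out of every safety table. The documents do not support that. Protocol 13.5.1 allows AE reporting when the event is worse than expected, and reported events enter the by-treatment AE tables. Events treated with systemic steroids as defined enter the exacerbation tables. Asthma worsening is a recorded withdrawal reason (Protocol 6.4.2). The eCRF bar on rescue covers only study-supplied albuterol/salbutamol, so ipratropium could appear among concomitant medications. What remains is that capture depends on judgement, treatment given or withdrawal, rather than on the measured fall.

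The missing-reading point is conditional. Protocol 8.3.1.1 has subjects monitored until 95% recovery, and the ITT derivation keeps readings after rescue. A deep 5-minute fall followed by readings on schedule is retained, and nothing in the plan calls for spirometry to stop early.

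Finally, the expected counts span more than a hundredfold and cannot show that the event will be common. That is correct.

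**Conclusion.** The point holds as a reporting gap: no planned display counts FEV₁ falls of 40% or more by treatment, and a fall reversed with albuterol reaches the safety tables only through site judgement, under AE wording that pulls both ways. No planned estimate, test or error rate is affected.

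The size is unknown. Under the stated assumptions it runs from about 0.1 to 24 challenges out of 168 per treatment, or about 0.6 to 5.6 subjects out of 56 at rates of 1% to 10%. The case for change rests on the protocol having named the event and set its threshold, not on those figures. The addition is worthwhile because it costs little and makes the report answer a question the protocol itself raises.

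**What to change.** Add one descriptive table to SAP Table 5 and SAP 10.13.5:

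- **Content:** number and percentage of subjects, and of challenges, with any acceptable post-challenge FEV₁ at or below 60% of that challenge's own pre-exercise value.
- **Layout:** by treatment and challenge (Day 1 at 23 hours, Day 14 at 12 hours, Day 14 at 23 hours), with the Visit 2 eligibility challenge shown separately.
- **Readings:** every acceptable post-challenge reading in the database, without requiring the readings at 17 minutes or earlier and at 25 to 50 minutes. The table should say that additional recovery readings count, because SAP 10.5.3 otherwise sends unplanned measurements to the listings.

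The SAP addition is enough. It needs no protocol amendment, no new data, no formal test, and no change to rescue, withdrawal or other clinical management. The cost is one extra table, which may hold few events and would then be imprecise.
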